4.6.3 Implementation data

Practice change facilitators: The collection of the implementation data will be undertaken through visits/contacts (approximately monthly) within the resources available depending on the final number of community pharmacies participating, by practice change facilitators employed as part of the project. An open-ended discussion which, depending on the mode of contact, will vary between 10 to 20 minutes (see Appendix 21 for an implementation checklist to be used by practice change facilitators). Data will be collected using a pre-developed form in REDCap. Practice change facilitators will be trained by an implementation expert on models and frameworks of implementation science with an emphasis on the application of these to this specific study and the use of the checklist for data collection purposes.

Semi-structured interviews: A purposive list of stakeholders with in-depth knowledge about the constraints and enablers to successful implementation of the model will be identified using a snowballing method. We will ensure a diverse range of stakeholders are included - general practitioners, and people from professional bodies including the Pharmacy Guild, Pharmaceutical Society of Australia and the Royal Australian College of General Practitioners, and NSW Health administrators. Potential participants will be approached directly by a member of the study team at the University of Newcastle and asked if they are willing to be approached for interview. Names of those willing to be contacted will be provided to the research team at the George Institute, who will provide the potential interviewee with participant information sheets and follow the informed consent process as for the other groups of participants.

The perspectives and experiences of community pharmacists and participants (patients) will be captured at 6 months using semi-structured interviews undertaken by The George Institute (Appendices 22 and 23). A maximum variation sampling technique will be used to select a diverse range of pharmacies and patients for interviews, taking into consideration pharmacy level factors such as geography, pharmacy size and participant level factors such as age, geography, presence of comorbid conditions, income status. It is anticipated that around 50 interviews in total will be conducted, however, the final sample size will be determined when it is considered the research team have achieved thematic saturation and few new themes are emerging from the interviews.

For participants (patients), interview questions will focus on experiences of health care and awareness and perceptions of services (Appendix 22). They will take no longer than 45 minutes. For community pharmacists and other stakeholders', questions will focus on implementation and contextual factors which may influence program outcomes [5-8], sustainability, staff experiences and motivation to engage in the prescribing model (Appendix 23). These interviews will take up to 1 hour.

Data collection will be conducted by members of the research team who are experienced in qualitative research methods. These sessions will take place via telephone, videoconferencing (e.g., Zoom or MS teams), or face-to-face at a community pharmacy, depending on the participants' preference and feasibility and other factors at the time. All sessions will be audio-recorded and transcribed and detailed field notes recorded.

4.7 Data management

Only authorised personnel acknowledged and approved by the Human Research Ethics Committees will have access to study data. All study files will be retained for a minimum of 15 years at respective study sites in accordance with the Australian Code for the Responsible Conduct of Research. The final evaluation dataset will be archived at the completion of the project resulting in a single primary data source being retained at the University of Newcastle.

4.7.1 Community pharmacy data

Participating pharmacies will record the patient consultation data in a software application (MedAdvisor) installed in each pharmacy. The data are stored centrally on a secure server hosted by MedAdvisor. MedAdvisor will generate an extract of community pharmacy data, and this will be transferred securely to the research team (University/The George Institute) via one of the following ways:

1. Shared via an AWS S3 and The George Institute/University provided with an Access Key/Secret Access
2. Machine-to-Human e.g., a csv that is sent via secure message platform Kiteworks.co

Data files will include patient identifiers, patient name, contact details and date of birth), the study identification number, and information collected at the registration visit. Upon receipt of data transfers, The George Institute and UoN research teams will store the data files on secure servers (more detail below).

4.7.2 Participant (patient/carer) self-reported data

Follow-up data will be collected on GDS case report forms hosted by The George Institute. Participants will be identified only by their study identification number and no identifying information will be collected on these forms.

4.7.3 Participant (patient/carer) interviews

Participants will be asked during their consenting process if they may be contacted by the research team with an invitation to participate in an interview. It is not expected that interview topics will cause any harm or distress to participants. During interviews if a participant does experience discomfort from the topics discussed or recollection of their health care experiences, they can ask to stop or pause the interview or skip any questions. If patient/carer participants raise any concerns or have question about symptoms or their health care, they will be directed to discuss this with their usual health care provider or a patient support line. To minimise inconvenience participants will be i) invited to complete the interview at a time best suited to them; ii) patients/carers will be offered a voucher of \$20 in recognition of the time taken out of their usual day to participate. Private providers such as Pharmacists and GPs will be offered a \$50 voucher for their time, while public health providers, and administrative and service managers will be interviewed within standard working hours, requiring no further compensation as standard practice.

4.7.4 Implementation data

Practice change checklists: Data from the checklists developed by Practice Change Facilitators will be entered into Redcap. A deidentified file including only pharmacy identification number will be securely sent by the UoN research team to the George Institute for analysis.

Interviews: Lists of patient participants that expressed they are willing to be contacted for an interview on the consent form will be generated. A diversity sample will be constructed from these lists to include a range of socio-economic status, living situation (independent/ other), morbidities and engagement with the initiative. Lists of health system administrators and providers will include those directly or indirectly involved in the initiative. The study team will contact eligible participants to invite them to participate and request a time for an interview (Appendix 24). Non-responding eligible participants will be followed up a maximum of two times. At the scheduled interview, all participants will be given a full explanation of the study by the research team and provided with an opportunity to ask questions. Consenting participants will be allocated the unique study

ID number generated at the baseline registration visit. Interview data will include files of audio and video recordings and transcripts of interviews. Audio or videoconference files of interviews will be transcribed verbatim by Digital & Audio Transcription Services (DAATS), an Australian company with 128-bit SSL servers based in Sydney, after a confidentiality agreement has been signed. Nevertheless, all data regarding interviews will be securely stored in TGI and UoN servers.

For participants who participate in interviews conducted by The George Institute, interviews will be recorded and transcribed. Transcriptions will be conducted by DAATS (Digital & Audio Transcription Services), an Australian company, in accordance with their [privacy policy](#) and [security policy](#). The George Institute's Privacy Policy can be found at: <https://www.georgeinstitute.org/privacy-policy>

4.8 Data flow and storage

Table 1 summarises the data sources and flow:

Data	Type	Source	Custodian	Flow	Ethics/ governance considerations
Community Pharmacy registration data	Identified, + participant study ID	Community pharmacy (MedAdvisor)	- MedAdvisor -The George Institute (TGI) -The University of Newcastle (UoN)	-MedAdvisor send identified data to TGI and UoN	-University of Newcastle (UoN) HREC approval -Data access agreement between UoN, TGI and MedAdvisor
Participant follow-up data	Deidentified, + participant study ID	GDS form hosted by TGI	-TGI -UoN	-Data retained by TGI and shared with UoN	-UoN HREC approval
Implementation data	Pharmacy ID Participant study ID	Community pharmacists and participants	-UoN -TGI	-Checklists entered into pre-prepared REDCap form -Interviews professionally transcribed and stored on UoN/TGI password protected server -Data retained by UoN/TGI and not sent to other parties	-UoN HREC approval

MedAdvisor is a ISO27001 credentialed company. This information security standard governs the company's handling of how personally identifiable information and health data is securely recorded and stored. Information is accessed by researchers via an extension of the company's information security management system and will be underpinned by a data sharing agreement. Functionally, researchers will be provided data via a secure machine to machine integration or a secure machine to human process. The company utilises the secure transfer software Kiteworks for this purpose. Pharmacy data is restricted within the pharmacy in alignment with the company's existing Pharmacy Licencing Agreement and the ISO27001 framework. The company offers on-premises software to support this data handling. Regarding the contractual arrangements between MedAdvisor and the two subcomponents, Foxo and Hola health, they are only permitted to Process Personal Data (and any other forms of Company Data) for the sole purpose of providing the Services and performing its obligations under this Agreement and the Contractor must not access or use the Personal Data

(or any other Company Data) for any other purpose (including for the Contractor's own purposes) without the Company's prior written consent.

The George Institute policies pertaining to the secure transfer and storage of study materials and data will be followed. TGI's secure infrastructure is physically located in an ISO 27001 certified data centre in Sydney. Technical controls include access via encrypted network connections, multi factor authentication, data storage on encrypted disks, encryption of all offsite backups, discretionary access controls on project data folders, micro-segmented next generation firewalls, together with a Security Information and Event Management system monitoring network traffic and scanning for Indicators of Compromise. Associated procedural controls are captured in standard operating procedures and Work Instructions.

Pharmacies, pharmacists, and patients will provide consent for data to be transferred from MedAdvisor to the research team.

4.9 Outcomes

Primary outcome

The primary outcome will be symptom resolution/relief (completely resolved, improvement, no improvement or worsening) (based on self-report at various time frames at follow up depending on the condition). This will be a composite measure based on patient self-reported data. As symptom resolution/relief time can be different for each of the four conditions, follow-up periods according to the clinical practice guidelines will be:

- 7 days for Impetigo, Psoriasis and Herpes Zoster (Shingles)
- 14 days for Atopic Dermatitis

Secondary outcomes

Secondary outcomes will be:

- Types of medication supplied for each condition by pharmacists. This is a participant specific outcome.
- Adherence rates to treatment protocol. This is a pharmacy-specific outcome.
- Numbers of patients supplied medications by pharmacists. This is a participant specific outcome.
- Numbers of patients provided self-care advice. This is a participant specific outcome.
- Numbers of patients referred to another health professional. This is a participant specific outcome.
- Reasons for patient referral to another health professional. This is a participant specific outcome.
- Estimated duration of consultation. This is a pharmacy specific outcome.
- Patient follow-up rate. This is a participant specific outcome.
- Patient adverse events. This is a participant specific outcome.
- Patient experience. This is a participant specific outcome.
- **Safety outcomes:** Patient-reported adverse events defined as any unfavourable and unintended sign, symptom or disease associated with the use of a medicine, which does not necessarily have to be caused by that medicine (Appendix 25).
- **Implementation outcomes**
 - Patient and provider program participation rates
 - Patient demographics (gender, DOB, education, employment status)
 - Numbers of patients per pharmacy assessed as eligible for pharmacy medication supply.
 - Numbers of patients supplied medication by pharmacists.
 - Estimated duration of consultation
 - Estimated time to complete all service requirements.
 - Adherence rates to treatment protocol
 - Prescriptions for first-line medications for the four skin conditions /Total medication prescriptions for the four skin conditions
 - Classification of appropriateness of medications for the four conditions as aligned with clinical practice guidelines.

- **Economic outcomes:** Results from the economic analysis will be expressed as (1) net benefit in terms of implementation costs and cost savings arising from more efficient treatment pathways; and (2) cost-consequence results accounting for patient experience measures, relevant safety outcomes and implementation measures.

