4.1 Study hypothesis

The study hypothesis is that the community pharmacy delivered services for four skin conditions will: (1) achieve high rates of implementation and adherence to treatment protocols; (2) result in self-reported symptom resolution/relief rates at various time interval depending on the condition; and (3) not be associated with safety risks.

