4.6.2 Participant (patient/carer) self-reported data from follow-up

Those assessed as eligible to participate in the trial will be followed up at different time frames depending on the condition. The follow up will include a brief survey administered by The George Institute either via SMS message or email with a link to a case report form using George Data Systems (GDS). Information will be collected on the primary outcome measure of symptom resolution/relief rate, any additional care provided, changes to treatment, service satisfaction and overall experience of care. Basic demographic (educational level, employment status, cultural status) and clinical information (condition, reason for consult, symptom description, other professional visits and other medications use) will also be captured. Appendix 20 provides the case report form for patient follow-up.

The follow up survey will be sent to patients by SMS and/or email, 7 or 14 days after the consultation depending on the condition. Up to 3 reminders will be sent to all patients that do not complete the survey at two, four and six days after the initial sending date. Patients that do not complete the survey after these reminders will be assumed as lost to follow up and will not be contacted further.

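### The safety outcome in section 4.9 counts only patient-reported events, routinely collected by one survey, and is narrower than the events the trial may come to know of

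*Protocol*

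**What the plan says.** Section 4.9 labels its safety outcome as "Patient-reported adverse events defined as any unfavourable and unintended sign, symptom or disease associated with the use of a medicine", adds that the medicine need not be the cause, and points to Appendix 25. The general list of secondary outcomes in the same section has a separate line, "Patient adverse events. This is a participant specific outcome", which names no reporter or source. Hypothesis 3 in section 4.1 is that the service will "not be associated with safety risks", and objective 3 in section 3.2.2 is to assess safety.

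Section 4.6.2 gives the timing of patient self-report: "The follow up survey will be sent to patients by SMS and/or email, 7 or 14 days after the consultation depending on the condition". After up to three reminders, "Patients that do not complete the survey after these reminders will be assumed as lost to follow up and will not be contacted further".

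Three other passages concern places where an event might surface:

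- Section 4.7.3, on interviews: "If patient/carer participants raise any concerns or have question about symptoms or their health care, they will be directed to discuss this with" their usual provider or a support line.
- Section 4.7.4, on the practice change facilitators' checklists: "A deidentified file including only pharmacy identification number will be securely sent by the UoN research team" to The George Institute.
- The data-flow table in section 4.8, on implementation data: "Data retained by UoN/TGI and not sent to other parties".

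Section 4.11 gives the DSMB the task of reviewing any serious adverse event in the study and of examining how often adverse events occur and how severe they are. It does not limit either task to patient reports.

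**The concern.** The definition fixes who must report an event for it to count. A pharmacist may see a patient return with a reaction, a facilitator may hear of one during the roughly monthly contact with a pharmacy, and the serious adverse event process may bring one to light. Unless the patient also reports it, the event does not meet the labelled safety outcome.

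At stake are objective 3 and hypothesis 3. The design is a cohort, and the text describes no comparison group in which incomplete capture might cancel out. The count of events is itself the safety evidence, so the report could state a figure lower than the number of events the trial team already holds on file.

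**Working it through.** **Setting the passages side by side**

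1. Section 4.9, safety outcome: the source is restricted to the patient.
2. Section 4.9, secondary outcome list: adverse events, with no source stated. The two lines may be meant as one outcome or as two; the text does not say.
3. Section 4.6.2: one survey. The listed content covers symptom resolution, further care, treatment changes, satisfaction and experience. Adverse events are not named there, though the form itself is Appendix 20 (not shown), and the questions on further care and other professional visits could bring some to light.
4. Section 4.6.2: non-responders are not contacted again. Section 4.4.1 also removes the data of participants who withdraw, with no stated exception for safety data.
5. Section 4.6.1, Table 3 (the pharmacist's form): no item for a later adverse event or a return visit.
6. Section 4.8, Table 1: no adverse-event row, and no row names the DSMB as a recipient.
7. Section 4.11: the DSMB's remit is wider than item 1.

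Items 1 and 7 do not match in scope. Items 3 to 6 show that the body text describes no path by which an event learned of from someone other than the patient enters the safety data.

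**How many events a survey alone could miss**

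The protocol states no event rate, response rate or precision for safety, so there is no figure of its own to reproduce. What follows is an illustration.

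- N = 22,857 consults, the ceiling in the synopsis, assumed to be reached with one survey per consult.
- p = true rate of a serious event, assumed 0.001.
- r0 = response among patients without an event, assumed 0.3 to 0.7.
- r1 = response among patients with an event = r0 × k, with k assumed 0.5 to 1.25.
- Every responder with an event is assumed to report it.

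True events = N × p = 22,857 × 0.001 = 22.9.

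Events seen = N × p × r1.

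Estimated rate among responders = p × r1 / (p × r1 + (1 − p) × r0).

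Worked case, r0 = 0.5 and k = 0.5: r1 = 0.25. Events seen = 22.857 × 0.25 = 5.7. Estimated rate = 0.00025 / (0.00025 + 0.999 × 0.5) = 0.00050, which is half the true rate.

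| k | Seen, r0 = 0.3 | Seen, r0 = 0.5 | Seen, r0 = 0.7 | Estimated rate per 1,000 (true 1.00) |
|---|---|---|---|---|
| 0.5 | 3.4 | 5.7 | 8.0 | 0.50 |
| 0.75 | 5.1 | 8.6 | 12.0 | 0.75 |
| 1.0 | 6.9 | 11.4 | 16.0 | 1.00 |
| 1.25 | 8.6 | 14.3 | 20.0 | 1.25 |

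Events are missed in every cell: between 2.9 and 19.4 of the 22.9. The estimated rate depends almost entirely on k. It is too low for k below 1, right at k = 1 and too high above 1. At p = 0.005 the pattern is the same: 17.1 to 100.0 of 114.3 events are seen.

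**The case against.** The strongest reply is that the protocol does not confine safety monitoring to the survey. The DSMB, and the Project Steering Committee until the DSMB is in place, review any serious adverse event. Section 4.9 lists adverse events a second time without restricting the source. Appendix 25 holds the adverse event policy and process, and the safety outcome itself refers to it. Appendix 21 (the facilitator checklist) and Appendix 20 (the survey form) are not shown either, and any of the three may contain what the body text lacks. Table 3 is a consultation form, so the absence of a field for later events is unsurprising. The interviews number about 50 in all and would add few events.

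Most of this stands, and it limits the point. It does not remove it. A remit to review events is not a definition of the reported outcome, and the labelled safety outcome would still count patient reports only, whatever process Appendix 25 sets out.

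A reader might infer that stated rules keep events told to facilitators or interviewers out of the safety data. The text does not support that. Section 4.7.3 tells staff where to direct a patient and is silent on recording. Section 4.7.4 de-identifies one transfer between the two institutions. The Table 1 entry is a custody statement, and Table 1 lists a participant study ID as well as a pharmacy ID for implementation data. Reading that entry as shutting out the DSMB proves too much, since no row of Table 1 names the DSMB.

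**Conclusion.** The point holds as a mismatch between a stated definition and the events the trial may know of. The safety outcome is limited to patient reports, the body text describes one survey to collect them, non-responders are not pursued, and the DSMB's remit is wider. The body text does not say how events learned of elsewhere reach the safety analysis.

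On size, at an assumed 1 per 1,000 and under the response assumptions above, the survey alone sees 3.4 to 20.0 of about 23 events. These are not predictions, because the rates and response fractions are all assumed.

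Two further inferences go beyond the documents. One is that the estimated rate is biased toward safety; the other is that patients with the worst outcomes are the most likely to be missed. Both need patients with events to respond less often than others. That is plausible for someone in hospital, but people who have been harmed may equally be keener to answer, and the protocol gives no response data either way.

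This should be changed, but it does not undermine the design. Confidence is moderate because Appendices 20, 21 and 25 are not shown.

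**What to change.** - **Section 4.9:** define the safety outcome as adverse events from any source known to the trial (patient survey, pharmacist, facilitator, interview, serious adverse event process), with the source recorded. Report the patient-reported count and the any-source count side by side. State whether the separate adverse-event line in the secondary list is the same outcome.
- **Facilitator and pharmacist forms:** add one adverse-event item carrying the participant study ID, if Appendices 21 and 25 do not already provide it.
- **Section 4.7.3:** add that a health concern raised at interview is also passed to the Appendix 25 process.
- **Section 4.8, Table 1:** add an adverse-event row that flows to the DSMB.

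Notifications from general practitioners or emergency departments are left out, because the protocol describes no inbound channel for them and a wording change would not create one.

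The cost is wording, up to two form items in systems already in use, and a protocol amendment approved by the ethics committee under section 5.3. No new visits are needed. The drawback is that any-source reporting will be less uniform across pharmacies than a standard survey. Showing both counts, with sources, makes that visible and keeps the patient-reported measure intact.
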